## Primary Safety Endpoint

Literature review through a random effect meta-analysis showed a 95% freedom from MAE at 30 days. The pre-specified performance goal for the primary safety endpoint is 85% based on an allowed 10% margin. The hypotheses are H0: Freedom from MAE at 30 days  $\leq$  85% vs. Ha: Freedom from MAE at 30 days > 85%. Under an exact, one-sided test for a single binomial proportion at the 0.025 significance level, a sample size of 102 mITT subjects will be required to provide at least 90% power to meet this primary safety objective.

## Overall Sample Size

In order to adequately power for both primary effectiveness and primary safety hypotheses, we require a sample size of 102 mITT subjects who complete 30 days follow-up. The dropout rate of mITT subjects is assumed to be 10 %. The final sample size for the study will be 112 subjects.

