In order to adequately power for both primary effectiveness and primary safety hypotheses, we require a sample size of 102 mITT subjects who complete 30 days follow-up. The dropout rate

of mITT subjects is assumed to be 10 %. The final sample size for the study will be 112 subjects.

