In case of missing data that is of concern at 30 days when the primary safety endpoint is evaluated, the probability of a subject achieving freedom from MAE at 30 days will be estimated using Kaplan-Meier method. The standard error will be approximated using Greenwood's formula. A two-sided 95% log-log confidence interval for the probability will be constructed. The Kaplan-Meier estimate and its 95% log-log confidence interval will be constructed from the day of index procedure through the 30 days follow-up. For subjects with MAE, days of follow-up will be computed as the days from the index procedure to the onset date of the first event. For subjects without MAE, days of follow-up will be computed as the days from the index procedure to the last follow-up at the time of data lock for primary analysis.

If the lower bound of this 95% confidence interval is greater than the performance goal 85%, we can conclude that the primary safety endpoint is met.

As a sensitivity analysis, a tipping-point analysis will be conducted. A tipping point is defined as the number of events in the missing cohort at which the study conclusion is changed. Let n_m be the number of missing values in the mITT cohort. Starting at 0 and ending at n_m , the event rate is changed by adding 1 event at a time. The 95% confidence interval will be calculated each time when adding 1 event.

The primary safety analysis will also be performed in the PP set as supportive evidence.

Analysis of Primary Effectiveness Endpoint

The primary effectiveness will be assessed by calculating the proportion of subjects who have achieved technical success over the mITT subjects. A 95% two-sided confidence interval will be estimated using the Clopper-Pearson interval (F-distribution method). If the lower bound of this 95% confidence interval is greater than the performance goal 86%, we can conclude the primary effectiveness endpoint is met.

The primary effectiveness analysis will also be performed in the PP set as supportive evidence.

Analysis of Secondary Endpoints

The secondary endpoints will be analyzed with descriptive statistics; there will be no formal statistical hypothesis test. Details of these statistical analyses will be provided in a separate standalone Statistical Analysis Plan.

Poolability of Investigational Sites

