## 6.2.2 Analysis of Primary Safety Endpoint

The analysis of primary safety endpoint (i.e., freedom from MAE at 30 days) will be performed in the mITT analysis set. The primary safey will be assessed by calculating the proportion of subjects who have no MAE at 30 days aggregated over the mITT subjects. A 95% two-sided confidence interval will be estimated using the Clopper-Pearson interval (F-distribution method). In this analysis, the denominator includes all subjects in the mITT set and subjects who have no events but have dropped out prematurely before 30 days will be assumed not to have experienced an event.

If the lower bound of this 95% confidence interval is greater than the performance goal 85%, we can conclude the primary safety objective is met.

Each component of the primary safety endpoint will be also analyzed in the similar fashion as the aggregated primary safety endpoint in the mITT set.

Clinically-driven TLR will be analyzed on a per-subject basis. For subjects with more than one lesions, if at least one of the lesions has a clinically-driven TLR, the subject will fail the endpoint. The date of the earliest clinically-driven TLR will be used as the basis of determining a failure for the K-M analysis.

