## 6.2.3 Alternative Analysis of Primary Safety Endpoint

In case of missing data of concern at 30 days when the primary safety endpoint is evaluated, the probability of a subject achieving freedom from MAE at 30 days will be estimated using Kaplan-Meier method. The standard error will be approximated using Greenwood's formula. A two-sided 95% log-log confidence interval for the probability will be constructed. The Kaplan-Meier estimate and its 95% log-log confidence interval will be constructed from the day of index procedure through the 30 days follow-up. For subjects with MAE, days of follow-up will be computed as the days from the index procedure to the onset date of the first event. For subjects without MAE, days of follow-up will be computed as the days follow-up will be computed as the days from the index procedure to the last follow-up at the time of data lock for primary analysis.

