## 6.2.4 Sensitivity Analysis of Primary Safety Endpoint

A total of three sensitivity/robustness analyses will be conducted to investigate how missing data impacts the primary analysis results if missing data are of serious concern.

- 1. Complete-Case: the complete-case method uses only the subjects who have completed the 30 days follow-up or have observed the success/failure status through 30 days.
- 2. Worse-Case: all subjects who have dropped out prematurely will be assumed to have experienced an event.
- 3. A tipping-point analysis will be conducted. A tipping point is defined as the number of events in the missing cohort at which the study conclusion is changed. Let nm be the number of missing values in the mITT cohort. Starting at 0 and ending at nm, the event rate is changed by adding 1 event at a time. The 95% confidence interval will be calculated each time when adding 1 event.

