## 6.2.5 Primary Effectiveness Endpoint

Primary effectiveness endpoint is technical success defined as the ability of the Cardio Flow FreedomFlowTM Orbital Circumferential Atherectomy System (Pneumatic and Electric) to achieve a residual diameter stenosis  $\leq$ 50% without adjunctive therapy, as assessed by an independent Angiographic Core Laboratory.

The primary effectiveness will be assessed by calculating the proportion of subjects who have achieved technical success over the mITT subjects. A 95% two-sided confidence interval will be estimated using the Clopper-Pearson interval (F-distribution method). If the lower bound of this 95% confidence interval is greater than the performance goal 86%, we can conclude the primary effectiveness objective is met.

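### The overall sample size does not reconcile: 112 subjects at 10% dropout leave about 101 who complete 30 days, not the 102 required; the effect is minor

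*SAP*

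**What the plan says.** SAP 4 sizes each primary test separately with an exact one-sided binomial test at 0.025: 102 mITT subjects for safety (95% expected against a goal of 85%, at least 90% power) and 101 for effectiveness (96% against 86%, 90% power). To cover both, the Overall Sample Size paragraph says "we require a sample size of 102 mITT subjects who complete 30 days follow-up", followed by "The dropout rate of mITT subjects is assumed to be 10 %. The final sample size for the study will be 112 subjects". Protocol 8.1 repeats the last step ("of mITT subjects is assumed to be 10 %. The final sample size for the study will be 112 subjects"), and so does the synopsis. None of the three places prints an inflation formula.

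The analyses treat dropout as follows:

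- **Safety, primary (SAP 6.2.2).** "the denominator includes all subjects in the mITT set and subjects who have no events but have dropped out prematurely before 30 days" are counted as having had no event. Protocol 8.3 does not contain this scoring rule.
- **Effectiveness, primary (SAP 6.2.5).** The method is "calculating the proportion of subjects who have achieved technical success over the mITT subjects". No rule is given for a missing or unreadable angiogram. The general rule in SAP 6.1.6 leaves a subject with a missing data point out of the affected analysis unless otherwise specified.
- **Safety, complete-case sensitivity analysis (SAP 6.2.4).** "the complete-case method uses only the subjects who have completed the 30 days follow-up or have observed the success/failure status through 30 days".
- **Safety, Kaplan-Meier.** SAP 6.2.3 invokes it "In case of missing data of concern at 30 days when the primary safety endpoint is evaluated", under the title of an alternative analysis. Protocol 8.3 uses nearly the same trigger ("In case of missing data that is of concern at 30 days when the primary safety endpoint is evaluated"), and there the sentence comparing the lower bound with 85% comes straight after the Kaplan-Meier interval.

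**The concern.** Dropout is stated as a rate among mITT subjects, so the number who complete is the mITT count times 0.90. Anyone who checks the paragraph will find that its three figures (102 completers, 10% loss, 112 subjects) cannot all hold.

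The shortfall is only 1.2 expected subjects. It deserves a look because 102 sits on a step of the exact safety test, where one subject fewer lowers power by several points. The paragraph also frames the requirement in completers, while the main primary analyses are defined on the mITT set. It therefore does not tell the reader what power those analyses have at 112, or which analyses dropout would weaken.

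**Working it through.** **Inputs.** From SAP 4 and Protocol 8.1: one-sided alpha 0.025, exact test; safety 95% against 85%; effectiveness 96% against 86%; 102 completers; 10% dropout; 112 subjects. From SAP 6.2.2 and 6.2.5: success means that the lower bound of the two-sided 95% Clopper-Pearson interval exceeds the goal.

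**1. The component sizes reproduce.** For each n, take the smallest success count r whose Clopper-Pearson lower bound exceeds the goal. Power is then P(X ≥ r) at the assumed rate.

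- Safety, n = 102: r = 94, power 93.0%. This is the smallest n from which power stays at or above 90%.
- Effectiveness, n = 101: r = 94, power 95.0%.

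**2. The dropout step does not.**

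- Completers from 112 at 10% loss: 112 × 0.90 = 100.8.
- Subjects needed for 102 completers: 102/0.90 = 113.3, so 114 (114 × 0.90 = 102.6).
- Loss that 112 can absorb: 112 − 102 = 10 subjects, and 10/112 = 8.9%.

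Two unprinted routes would give 112: 102 × 1.10 = 112.2, and 101/0.90 = 112.2, each rounded down. Which was used, if either, cannot be told from the documents.

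**3. Power with all 112 mITT subjects analysed.**

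| Test | Successes needed | Lower bound at r | Lower bound at r − 1 | Power |
|---|---|---|---|---|
| Safety, goal 85% | 103 of 112 | 85.29% | 84.19% | 94.6% |
| Effectiveness, goal 86% | 104 of 112 | 86.41% | 85.29% | 96.4% |

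The chance of meeting both is at least 0.9456 + 0.9639 − 1 = 0.9095, about 91%, whatever their dependence.

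**4. Safety power on the completer basis.** Clopper-Pearson rule, true rate 95%:

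| Completers | Successes needed | Power |
|---|---|---|
| 100 | 93 | 87.2% |
| 101 | 94 | 86.7% |
| 102 | 94 | 93.0% |

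Because power moves in steps, the average is the fairer summary. With completers distributed as Binomial(N, 0.90), mean safety power is 89.8% from N = 112 and 90.6% from N = 114, a difference of 0.8 points.

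**5. Kaplan-Meier, log-log interval with Greenwood's standard error.** The result depends on when dropouts leave.

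- All 11 leave before any event: 101 at risk, at most 7 events allowed, power 86.7%.
- All events precede the dropouts: 112 at risk, at most 9 events allowed, power 94.6%.

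With 102 at risk the log-log bound still allows only 7 events, and power is 86.1%. In the unfavourable case, delivering 102 completers would therefore not restore 90% for this method.

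**The case against.** The strongest reply is that nothing of substance is wrong. The gap is 1.2 subjects, and 112 is within two of 114. SAP 4 sizes both tests on mITT subjects before completers are mentioned. Planning for 102 completers while analysing every treated subject is conservative and is not a contradiction. Most of this stands, and it is why the point is one of wording. It does not make the paragraph correct: a stated number of completers is not delivered at the stated loss rate.

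Two stronger readings are tempting, and the documents support neither.

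- **A reader might infer that the trial is underpowered.** SAP 6.2.2 keeps dropouts in the safety denominator and SAP 6.2.5 refers to the mITT subjects. At 112 mITT subjects both tests exceed 90% power under the stated rates.
- **A reader might infer the opposite, that dropout cannot touch any primary test.** That is too absolute. In Protocol 8.3 the 85% decision sentence follows the Kaplan-Meier interval, so that analysis can be read as deciding safety when missing data are of concern. For effectiveness, SAP 6.2.5 does not override the general exclusion of missing data in SAP 6.1.6, so a missing angiogram could reduce n.

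Counting event-free dropouts as successes raises a separate question of bias. Changing 112 to 114 would neither cause nor cure it.

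**Conclusion.** The inconsistency is real and minor: at 10% loss the plan delivers about 101 completers against the 102 it requires, and 102 is reached only with losses of up to 10 subjects (8.9%).

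The Clopper-Pearson tests keep about 94.6% power for safety and 96.4% for effectiveness, on these assumptions:

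- The true rates are 95% and 96%, and for safety the 95% holds with event-free dropouts counted as having no event.
- Every core-laboratory angiographic result is available.
- There are 112 mITT subjects. Protocol 6.3 counts a subject as enrolled only once the device is attempted, but Protocol 6.2 and 6.5.1 count enrolment earlier, so 112 enrolled could mean fewer than 112 mITT.

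On the completer basis, safety power averages 89.8%, just under the stated 90%, and is 86.7% at exactly 101. This bears on the complete-case analysis. That analysis also keeps subjects whose status through 30 days was observed, so its n may exceed the number of completers. Dropout before day 30 can also weaken the Kaplan-Meier analysis.

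**What to change.** Keep 112 and add no patients.

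1. In the synopsis, Protocol 8.1 and SAP 4, replace the 10% dropout statement with wording such as: 112 mITT subjects allow up to 10 losses (8.9%) while leaving 102 with completed 30-day follow-up; at 10% loss about 101 complete.
2. In SAP 4 only, add that the primary Clopper-Pearson analyses use the mITT set. Give their exact power at 112: about 94.6% for safety, if the 95% rate holds with event-free dropouts scored as in SAP 6.2.2, and about 96.4% for effectiveness, if all core-laboratory results are available. This belongs in the SAP because the scoring rule appears only there.
3. Do not add a statement that dropout cannot affect a primary test.
4. If a completers-only power is quoted, give the average over random 10% dropout (about 90%), because the value at a single n depends on where it falls on the steps of the exact test.

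The cost is a short wording change in three places, with no change to endpoints, analysis sets or decision rules. The downside is that the stated loss allowance falls from 10% to 8.9%.

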## 5 ANALYSIS SETS

The primary analysis for effectiveness and safety will be based on a modified intent-to-treat principle. The per-protocol analysis set is designated as supportive.

Intent-to-Treat (ITT): the ITT set will be comprised of all subjects who have signed informed consent, meet all the inclusion and none of the exclusion criteria.

Modified Intent-to-Treat (mITT): the mITT set will be comprised of all ITT subjects who have the investigational device attempted.

Per-Protocol (PP): the PP set will be comprised of all subjects in the mITT set who have no major protocol deviations. All major protocol deviations will be reviewed and finalized before the data lock for final analysis.

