8.2 ANALYSIS SETS

The primary analysis for effectiveness and safety will be based on a modified intent-to-treat principle. The per-protocol analysis set is designated as supportive.

Intent-to-Treat (ITT): the ITT set will be comprised of all subjects who have signed informed consent, meet all the inclusion and none of the exclusion criteria.

Modified Intent-to-Treat (mITT): the mITT set will be comprised of all ITT subjects who have the investigational device attempted.

Per-Protocol (PP): the PP set will be comprised of all subjects in the mITT set who have no major protocol deviations. All major protocol deviations will be reviewed and finalized before the data lock for final analysis.

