10.1.2 Monitoring Visit

The following factors will be taken into account when determining the frequency of the monitoring visits: subject accrual rate at each center, total number of subjects enrolled at each center, and Clinical Investigation Plan compliance at each center. It is anticipated each site will be monitored at least once upon the completion of the 30-day follow-up visits for all enrolled subjects at the study site. Monitors will require direct access to subjects' medical records pertinent to the study (and study inclusion criteria), study management documents, regulatory documents and Subject Informed Consent documents, as well as other potential applicable records not listed here.

Monitors may ensure the clinical investigators have and continue to have staff and facilities to conduct the clinical investigation safely and effectively. Monitors may conduct the following monitoring activities throughout the study:

- Verification that the current IRB-approved informed consent was signed and dated by each subject prior to participating in the study required procedures.
- Verification of documentation in the subject's record that informed consent was signed prior to initiation of the study procedures and that a copy of the signed and dated consent was provided to the subject.
- Source documentation verification by reviewing the CRFs against source documentation for accuracy and completeness of information.
- Verification that the investigation is conducted according to the Clinical Investigation Plan, Instructions for Use and, all malfunctions/ IFU deficiencies are reported as required.
- Verification that subjects met study enrollment criteria.
- Verification that study deviations are documented and reported.
- Verification that the procedures for recording and reporting adverse events to the sponsor are followed.
- Ensuring proper error correction.
- Verification of training documentation of all study personnel participating in study related activities.
- Reviewing all correspondence and regulatory documents, including confirmation of IRB-approved Clinical Investigation Plan or amendments.
- Resolution of outstanding issues and completion of assigned tasks will be documented by the monitors.

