12 STUDY ADMINISTRATIVE OVERSIGHT

12.1 CORE LABORATORY

Independent core laboratories shall be utilized to provide a standardized process and assessment of all angiographic and duplex ultrasound studies. The core laboratories will be responsible for analyzing the angiograms and ultrasound images according to the study eligibility criteria, the study endpoints and this study protocol, for providing feedback to the sites and Sponsor regarding

⁰¹⁰⁻⁰⁵⁵ Protocol Version F

the quality of the tracings and images and for providing a written summary report of all angiograms and duplex ultrasound results to the study Sponsor.

Investigators will enroll subjects into the study based on inclusion and exclusion criteria. Lesion characteristics and measurements will be assessed by investigators using visual estimates; however, the core laboratory will assess by quantitative angiography. Baseline measurements and post-procedure results will be reported by the investigator and by the core laboratory.

Angiographic and Vascular Ultrasound Core Laboratory Protocols shall be provided to the investigational sites.

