12.9 PROTOCOL DEVIATIONS / VIOLATIONS AND MEDICAL EMERGENCIES

A protocol deviation or violation is a failure to comply with the requirements of the clinical study as specified in the protocol. Examples of protocol deviations include late visits, missed visits, required follow-up testing not completed. An example of a major protocol violation includes enrollment of a study subject who fails to meet inclusion/exclusion criteria as specified in the protocol. Each investigator shall conduct this clinical study in accordance with the study protocol and any conditions required by the reviewing IRB.

Deviations/violations from clinical protocol requirements will be reviewed and evaluated on an ongoing basis and, as necessary, appropriate corrective actions put into place. See Table 12-1: Reports Required from Investigators to Sponsor for reporting timelines for emergency deviation.

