## 6.2 **Primary Endpoints**

The study will be considered a success if both primary effectiveness and safety objectives are met using the mITT Set at the one-sided 0.025 level of significance in the final analysis. The primary endpoint analyses will also be performed in the PP set as a supportive evidence. The primary endpoint analyses will also be performed in the mITT and PP sets by product power type (Pneumatic System and Electric System).

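### ITT, mITT and PP all require every eligibility criterion to be met, so a treated subject later found ineligible drops out of both primary analyses and the adverse event tables

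*SAP*

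**What the plan says.** Protocol 8.2 and SAP 5 define the sets identically, as a chain:

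- ITT: "the ITT set will be comprised of all subjects who have signed informed consent, meet all the inclusion and none of the exclusion criteria".
- mITT: "the mITT set will be comprised of all ITT subjects who have the investigational device attempted".
- PP: the mITT subjects without major protocol deviations. On timing: "All major protocol deviations will be reviewed and finalized before the data lock for final analysis".

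SAP 6.2 rests the trial's conclusion on mITT: "The study will be considered a success if both primary effectiveness and safety objectives are met using the mITT Set". Secondary endpoints also use mITT (SAP 6.3). Adverse event analyses use ITT (SAP 6.4), which also promises a by-subject listing of all adverse events. Neither document defines an as-treated or safety set.

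Protocol 12.9 expects that ineligible subjects may be enrolled: "An example of a major protocol violation includes enrollment of a study subject who fails to meet inclusion/exclusion criteria". Protocol 10.1.2 anticipates that "each site will be monitored at least once upon the completion of the 30-day follow-up visits for all enrolled subjects" at the site, and lists among the monitoring activities "Verification that subjects met study enrollment criteria". Protocol 12.1 adds: "The core laboratories will be responsible for analyzing the angiograms and ultrasound images according to the study eligibility criteria".

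**The concern.** The eligibility condition sits in the outermost set, so every other set inherits it. A subject who received the device and is later found to have breached a criterion has no place in the set that decides success or in the adverse event summary tables. Protocol 12.9 calls such an enrolment a major violation, which is what PP exists to remove, yet under these definitions the subject was never in mITT.

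Timing makes this more than untidy. The minimum monitoring described in 10.1.2 falls after the 30-day visits, when the safety outcome is known. The angiographic core laboratory that reads technical success also reads images against the eligibility criteria. With no control arm, nothing offsets a selective removal of treated subjects, and both primary results are judged against fixed goals.

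The protocol also contains one possible route to such a subject. Section 6.5.2 allows a non-target limb to be treated at least a week before the index procedure, whereas exclusion criterion 9 bars a non-index-limb procedure within 2 weeks before it. A site following 6.5.2 could enrol someone who fails criterion 9.

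**Working it through.** **Inputs from the documents.** Performance goals are 85% (safety) and 86% (effectiveness); planned rates are 95% and 96%; the test is exact, one-sided at 0.025, read from the two-sided 95% Clopper-Pearson lower bound; planned mITT sizes are 102 and 101; total enrolment is 112 (Protocol 8.1 and 8.3; SAP 4, 6.2.2 and 6.2.5).

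**Inputs assumed.** All 112 are treated. The number of ineligible treated subjects, *m*, and their success rate, *q*, are not in the documents and are varied below.

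**1. The plan's own figures.** At n = 102 the safety test passes with at most 8 MAEs: exact alpha 0.0231, power 93.0%. At n = 101 power is 86.7%, so 102 reproduces. For effectiveness at n = 101, at most 7 failures are allowed: alpha 0.0214, power 95.0%, which meets the stated 90%. At n = 112 the limits are 9 MAEs and 8 technical failures.

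**2. Boundary cases.** The lower bound for x successes in n is the 0.025 quantile of Beta(x, n − x + 1).

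| Endpoint (goal) | All treated kept | After exclusion |
|---|---|---|
| Safety (85%), one MAE subject dropped | 102/112: 84.19%, fails | 102/111: 85.17%, passes |
| Effectiveness (86%), one technical failure dropped | 103/112: 85.29%, fails | 103/111: 86.29%, passes |
| Safety (85%), three event-free subjects dropped | 103/112: 85.29%, passes | 100/109: 84.90%, fails |

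Under the planned rates, exactly 10 MAEs in 112 has probability 2.95%, and exactly 9 technical failures 2.15%. These are the chances of landing on the boundary, not of a changed conclusion. If one subject is ineligible and fares like everyone else, the chance of turning a failure into a pass is 0.0295 × 10/112 = 0.26% for safety and 0.0215 × 9/112 = 0.17% for effectiveness.

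**3. False-pass rate when the all-treated rate is exactly at the goal (PG).** With *m* ineligible subjects at rate *q*, the eligible rate is r = (112 × PG − m × q)/(112 − m). For safety with m = 6 and q = 50%: r = (95.2 − 3)/106 = 0.870. At n = 106 the test passes with at most 8 MAEs or 7 technical failures.

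| Endpoint, m = 6 | q | Excluded | Kept |
|---|---|---|---|
| Safety | 85% | 1.6% | 2.1% |
| Safety | 70% | 2.8% | 2.0% |
| Safety | 50% | 5.6% | 1.8% |
| Effectiveness | 86% | 1.4% | 1.9% |
| Effectiveness | 70% | 2.6% | 1.8% |
| Effectiveness | 50% | 5.3% | 1.6% |

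Because counts are discrete, the result is not smooth in *m*. With m = 2 and q = 80%, the safety figure after exclusion is already 2.6%. In every case shown, 2.5% is exceeded only when the ineligible subjects do worse than the goal.

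**The case against.** The strongest reply is that eligibility means eligibility as judged at enrolment. Protocol 6.5.1 refers to the investigator's determination at the time of the procedure, 12.1 has investigators enrol on visual estimates, and 12.9 only makes sense for PP if ineligible subjects are already in mITT. On that reading the defect is one missing phrase. But the phrase is missing: the wording in 6.5.1 concerns angiographic screen failures before the device is used, it is not carried into the set definitions, and Protocol 6.3 repeats the literal condition for official enrolment.

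Several narrower points stand and limit the concern:

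- Stenosis and vessel diameter are defined by visual estimate, so a different core laboratory measurement does not by itself make a subject ineligible on those two. Total lesion length, occlusion length, in-stent restenosis, aneurysmal vessel, thrombus and the timing of earlier procedures carry no such qualifier.
- The visit after the 30-day follow-ups is a minimum. Protocol 10.1.1 also lists interim visits, and 12.9 has deviations reviewed on an ongoing basis. Late eligibility checks are permitted rather than certain.
- The sentence on finalising deviations belongs to the PP definition, and finalising before lock is a safeguard. No equivalent rule fixes when eligibility for mITT is settled.
- Adverse events are still recorded, endpoint events are still adjudicated, and the by-subject listing may show them. What is lost is their place in the summary tables and the primary rates.
- At the planned rates exclusion often works against the sponsor. With three ineligible subjects at 95%, safety goes from pass to fail about 4.2% of the time and from fail to pass about 0.06%.
- The false-pass figures take the all-treated rate as the target. If the target were eligible subjects only, the rate at the goal with n = 106 would be 1.6% and 1.4%. However, a set described as modified intent-to-treat is normally meant to cover those in whom treatment was attempted.

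**Conclusion.** The concern holds. Read literally, both documents place a treated but ineligible subject outside the primary, secondary and per-protocol analyses and outside the adverse event tables, and this conflicts with Protocol 12.9. The direction and size of any bias are unknown, because the number of such subjects and their outcomes are not given. One subject can change either conclusion at the boundary. The false-pass rate rises to about 5% only under strong assumptions: 6 ineligible subjects of 112, half of them failing, with the all-treated rate at the goal. If ineligible subjects fare like the others, a change from failure to pass is rare. The sample size is unaffected. This should be fixed because it concerns the set that decides success, and membership of that set should not turn on checks that can be made after outcomes are known.

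**What to change.** - In Protocol 8.2 and SAP 5, define mITT as all consented subjects in whom the investigational device is attempted, regardless of any later finding on eligibility, and no longer as a subset of an eligibility-conditioned ITT set.
- Remove eligibility violations only in PP.
- In SAP 6.4, present the adverse event summary tables in the device-attempted set.
- Separately, reconcile Protocol 6.5.2 (at least a week) with exclusion criterion 9 (2 weeks). Which interval applies is for the sponsor to settle.

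The cost is wording in Protocol 8.2 and SAP 5 and 6.4, made before data lock, plus the separate reconciliation. No new data are needed. The primary rates may be slightly less favourable if ineligible subjects did worse than the rest.
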